1.0 Objectives/Specific Aims

(Overall background of this technology and this proposal at MUSC now: LIFUP is an interesting new form of brain stimulation that promises to be the 'holy grail' of brain stimulation.(1-3) That is, it may be possible to stimulate non-invasively, safely, deep in the brain with focal precision. If true then we would have a new technology with enormous research and clinical potential. Currently transcranial magnetic stimulation (TMS), which is FDA approved for treating depression and OCD, can only stimulate the surface of the brain and can only stimulate deeper by increasing the intensity, and spreading the field. It is thus not deep and focal but deep and broad. In contrast, deep brain stimulation (DBS), which is FDA approved for treating Parkinson's Disease, can stimulate deep in the brain and quite focally. However, it is invasive and requires brain surgery and an implanted wire. There are surgical risks as well.

The LIFUP device was initially tested in animal models and was shown safe. The FDA then required testing in epilepsy patients who were going to have resection. The group at UCLA did this and examined the tissue for any short-term damage caused by the ultrasound. There was none. Thus, the FDA now treats LIFUP like diagnostic ultrasound and the UCLA IRB has approved several studies in healthy adults and other diseases. The UCLA data in healthy adults (thalamus) were presented last week and are attached in a poster.

The BSL at MUSC is a world leader in brain stimulation and we are excited about this technology. With the approval of IRB II we were the first in the world to perform TMS in the MRI scanner. We hope to become a world leader with this new technology. As our first test, we have chosen to use a pain paradigm within the MRI scanner. [name] perfected this method years ago and we have used it now in many studies. We will deliver the LIFUP to the thalamus and test whether the thalamus is involved with pain processing and whether LIFUP can alter that. We are experienced at doing pain studies in the scanner. We will get valuable experience with LIFUP with this study and then will likely use it in later studies in depression, anxiety, craving and addiction, etc.

When I first proposed to do TMS in the scanner over 20 years ago the MUSC IRB required that I be the first test subject, and report back. I did that and am prepared to do that here if that is what is needed. I think this LIFUP is as safe as diagnostic ultrasound, and has enormous research and clinical potential.)

Specific Aims.

- Aim 1.** Test the safety and feasibility of LIFUP to thalamus in healthy volunteers.
- Aim 2.** Characterize the time course and magnitude of thalamic LIFUP-induced analgesia.
- Aim 3.** Identify the brain circuitry (BOLD activity) that thalamic LIFUP changes during induced pain.

Hypothesis.

The anterior nuclei of the thalamus in addition to periaqueductal gray (PAG) and rostral ventromedial medulla (RVM) are integral regions of a supraspinal opioidergic structure that regulate pain perception (4-8). With the capability to influence deep neurological tissues, low intensity frequency ultrasound pulsation can likely modulate this circuit and induce analgesia. LIFUP deep brain modulation is achieved by induction of focused mechanical waveforms that traverse the cranium and underlying brain tissue (19). The low frequency of the ultrasonic wave consequently alters neuronal transmission and causes action potential variations through mechanical means, rather than thermal (20). The purpose of this study is to examine whether stimulation of the anterior nuclei of the thalamus via LIFUP induces analgesia. **We hypothesize that suppression of the anterior nuclei of the thalamus will induce a temporary increase**

in pain tolerance. Moreover, the behavioral changes in pain will correlate with specific regional BOLD changes during pain.

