Researchers have examined the effects of LIFUP in preclinical and clinical settings, confirming its ability to safely stimulate neural tissue⁽¹¹⁻¹⁴⁾, proposing cellular mechanisms for its efficacy⁽¹³⁻¹⁹⁾, and now using LIFUP in human patients⁽²⁰⁾. Monti et al. (2016) described a case study in which they used LIFUP to stimulate a comatose patient's thalamus.⁽²⁰⁾ Two pre-LIFUP assessments rated the patient as being in minimally conscious state (MCS). After sonication, the patient recovered motor and oromotor functions the next day, advancing to full language comprehension and communication by nodding and shaking his head. Five days post-LIFUP, the patient attempted to walk. While this study was neither blinded nor sham-controlled, the first application of therapeutic LIFUP in a human patient was encouraging and we expect more therapeutic applications of LIFUP and potential clinical trials in the future. If LIFUP continues to show clinical potential, it has the potential to supplant the role of DBS without the need for surgery. The key barrier to LIFUP replacing DBS for clinical applications is that by and large, DBS is used in a manner where the device is inserted and turned constantly on without attempting to fundamentally change circuit dynamics or behavior so that you could remove the device. Obviously, patients cannot permanently wear a LIFUP helmet. However, to the degree that we learn how to stimulate in ways that permanently change circuit behavior (LTD or LTP) without ablation, we may be able to substitute several sessions of LIFUP that can train and rewire the brain instead of permanently implanting hardware. LIFUP can certainly stimulate deep and focal and noninvasively and thus may be a key next step in the field of brain stimulation.

Information on the intervention to be studied.

We will be using the Brainsonix Low intensity focused ultrasound pulsation device. (BX Pulsar 1001). Please see the manufacturers description (Technical Summary) along with appendixes about the actual safety of the device itself.

FDA Status of the BX Pulsar 1001 device.

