10.0 Study Design/Methods

10.1. Study Design. Twenty healthy volunteers between 18-65 years of age without history of depression or chronic pain will be recruited to participate in this sham-controlled, double-blind crossover study, all within one session within the MRI scanner. All participants will receive 10 minutes of sham LIFUP, 20 minutes of rest, and 10 minutes of real LIFUP within the MRI scanner using the BXPulsar 1001, Brainsonix Inc. The order will be counterbalanced. The duration of the LIFUP analgesia and BOLD effects will be determined.

10.2. Behavioral Measures. We will begin baseline pain assessments by administering cutaneous hot and cold stimuli via the Medoc Pathway System (Medoc, Durham, NC) using a 30 x 30 mm ATS thermode. There will be two behavioral measures: quantitative sensory testing (QST) on untreated skin and blocks of pain on capsaicin-treated skin.

QST will be done using method of limits testing on the thenar eminence of the right hand. A program will be set up to administer 10 hot stimuli with random durations between each trial. The ATS thermode begins at 32°C and increases by 0.5°C per second. Participants will be asked to press a button in order to signify three different measures: (1) sensory threshold, or the temperature at which the stimulus becomes noticeable, (2) pain threshold, or the temperature at which the stimulus becomes painful, and (3) pain tolerance, or the temperature at which the stimulus becomes too painful to tolerate. Measuring these thresholds will yield information about

A β , A δ , and C fibers, respectively. The device will be set to stop heating at 51.5° C and stop cooling at 0° C to avoid tissue damage. These ten trials will be performed once before and once after each scanning block, either with thalamic LIFUP or 'fake' thalamic LIFUP.

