12.0 Data Management

The behavioral pain measures will be examined using a repeated measures ANOVA with time and condition (LIFUP, sham) as between group variables. These will be paired data within each subject.

Justification of Sample Size: Prior studies by our group using this same paradigm have shown differences in pain intensity with prefrontal TMS, or blocking of opiates. (29)

Consent procedures will be carried out within a private room inside the IOP. Data acquisition will be performed within the MUSC CBI research scanner at [name] The data will not be labeled with identifiable information. Participants will be identified on all research records solely by a number, ensuring confidentiality of all data. Any information that is obtained in connection with this study and that could identify the participants will remain confidential and will not be released or disclosed without their further consent, except as specifically required by law. If the results of this research are presented at scientific meetings, participant identity will not be

disclosed. All conversations with participants will take place behind closed doors in front of only the participant and designated caregivers, family, or friends.

Any imaging or other research data will be stored in a de-identified manner.

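### A rise in button-press pain tolerance cannot by itself be told apart from a general delay or sensory loss, and the plan does not use the sensory threshold it already collects as a control

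*Combined protocol and SAP*

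**What the plan says.** - **Purpose and hypothesis (section 1.0, Hypothesis).** The study is to examine "whether stimulation of the anterior nuclei of the thalamus via LIFUP induces analgesia". The prediction reads "We hypothesize that suppression of the anterior nuclei of the thalamus will induce a temporary increase", and the sentence ends by naming pain tolerance as what increases.
- **Measurement (section 10.2, QST).** "Participants will be asked to press a button in order to signify three different measures": sensory threshold, pain threshold and pain tolerance. The first is defined as "sensory threshold, or the temperature at which the stimulus becomes noticeable". All three are described on one ramp: "The ATS thermode begins at 32°C and increases by 0.5°C per second". Heating stops at 51.5 °C. QST is done before and after each scanning block, real or sham. The only use given for the three thresholds is that they inform on different nerve-fibre classes.
- **Other behavioural measure (sections 4.1 and 10.2).** The primary endpoint is pain ratings. Section 10.2 includes a 1 to 10 rating after each 22 s heat block at a fixed, individually set temperature, 12 times per scan.
- **Analysis (section 12.0).** "The behavioral pain measures will be examined using a repeated measures ANOVA", with time and condition as factors. The section names no contrast between thresholds and no check on response time or attention. It gives no rule for reading a result in which the sensory threshold also rises.

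**The concern.** On a rising ramp, the recorded temperature is the temperature at the moment of the press. Anything that postpones the press raises it: a slower hand, less attention, or duller heat sensation in general. None of these is analgesia.

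Randomised order, blinding and sham protect against expectation and drift. They do not protect here, because a delay or numbness produced by sonication would be a true difference between real and sham. The ANOVA would detect it correctly, and the hypothesis as worded would count it as support.

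The study already collects a non-painful measure with the same press and ramp. A general delay should move the sensory threshold as well, whereas a pain-specific effect should leave it largely alone. The plan does not say that this comparison will be made. If it is chosen after the results are seen, it will carry less weight.

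**Working it through.** **No plan figure to reproduce.** Section 12.0 supports the sample size by reference to earlier studies only. It gives no effect size, SD, alpha or power for the behavioural analysis.

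**Inputs from the protocol.** Ramp of 0.5 °C per second from 32 °C, with a cut-off at 51.5 °C (section 10.2). N is 20 in section 10.1 and 35 in section 6.0; that discrepancy is a separate matter, and both values are used.

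**Assumptions (not in the documents).** SD of the within-person real-minus-sham tolerance difference: 0.5, 1.0 or 2.0 °C. Added delay under real LIFUP: 0.2, 0.5 or 1 s. Two-sided paired t test at 0.05, and no change in pain.

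**Step 1: shift per delay.** Shift = 0.5 × delay, so 0.2 s gives 0.10 °C, 0.5 s gives 0.25 °C and 1 s gives 0.50 °C. The full ramp lasts (51.5 − 32)/0.5 = 39 s.

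**Step 2: chance of a significant real-versus-sham difference.** Noncentral t with n − 1 degrees of freedom and noncentrality (shift/SD) × √n. For example, 1 s with SD 1.0 °C and n=20 gives 0.5 × √20 = 2.24, and a rejection probability of 56.5%.

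| Delay | n | SD 0.5 °C | SD 1.0 °C | SD 2.0 °C |
|---|---|---|---|---|
| 0.2 s | 20 | 13.6% | 7.1% | 5.5% |
| 0.2 s | 35 | 21.0% | 8.9% | 6.0% |
| 0.5 s | 20 | 56.5% | 18.6% | 8.3% |
| 0.5 s | 35 | 82.0% | 30.1% | 11.1% |
| 1 s | 20 | 98.9% | 56.5% | 18.6% |
| 1 s | 35 | nearly 100% | 82.0% | 30.1% |

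These are two-sided rejection rates, so the figure with no delay at all is 5%.

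**Step 3: delay that would mimic a detectable effect.** The difference detectable with 80% power is 0.66 SD at n=20 and 0.49 SD at n=35. Dividing by 0.5 °C per second gives 0.66, 1.32 and 2.64 s at n=20 for SD 0.5, 1.0 and 2.0 °C. At n=35 it gives 0.49, 0.97 and 1.95 s.

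**Step 4: what the contrast does.** Take tolerance change minus sensory-threshold change, with a common 1 s delay, no analgesia and SD 1.0 °C for each. In 20,000 simulated trials, tolerance alone was significant in about 56% at n=20 and 82% at n=35. The contrast was significant in about 5% at both, because a common delay cancels.

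**Step 5: what the contrast costs.** With k the ratio of the sensory-threshold SD to the tolerance SD and r their correlation, the SD ratio is √(1 + k² − 2rk).
- k = 0.5, r = 0: √1.25 = 1.12, or 12% wider.
- k = 0.5, r = 0.5: √0.75 = 0.87.
- k = 1, r = 0: √2 = 1.41, or 41% wider.
- k = 1, r = 0.5: 1.00.

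For a true effect of 0.66 °C with SD 1.0 °C at n=20, tolerance alone has 80% power. With equal SDs, the contrast has 51% at r = 0 and 80% at r = 0.5.

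**The case against.** **No evidence of slowing.** A reader might infer from section 3.0 that the protocol itself shows thalamic LIFUP altering motor function, so that slower pressing is to be expected. The documents do not support that. The case reads "After sonication, the patient recovered motor and oromotor functions the next day": one minimally conscious patient, in a report the protocol describes as unblinded and without sham. The change was an improvement. If it carried over to healthy volunteers at all, faster pressing would lower tolerance temperatures and work against the hypothesis. Section 3.0 also mentions suppressed visual evoked potentials after focused ultrasound. That shows a non-pain sensory effect is conceivable, but it is neither slowing nor loss of heat sensation. This objection stands: the concern rests on how tolerance is measured, not on reported harm to motor function.

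**The primary endpoint is pain ratings.** Ratings at a fixed temperature do not depend on when a button is pressed, so they are a planned check on press delay. This stands too. They do not exclude numbness or inattention, which could lower ratings as well, and the hypothesis in section 1.0 is about tolerance.

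**The plan may not misuse the sensory threshold.** A reader might infer that a raised sensory threshold would be counted as further evidence of analgesia. No text says so. Section 10.2 keeps the three thresholds distinct by fibre class, and section 12.0 does not list which variables are the behavioural pain measures. What is missing is a stated use as a control.

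**The contrast is imperfect.** Sensory loss need not move a threshold near the ramp's start and a tolerance temperature by the same number of degrees. The 51.5 °C cut-off can cap tolerance but hardly the sensory threshold, which would shrink the difference. Requiring the contrast to be positive before any claim of analgesia could therefore reject a real effect. This is a sound reason to make it supportive and not a gate.

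**Conclusion.** The point holds as a gap in interpretation. A tolerance rise under real LIFUP would fit the stated hypothesis whether it came from analgesia, delay, inattention or general sensory loss. The plan prespecifies no use of the sensory threshold to help separate them.

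The size is conditional, since neither the delay nor the SD comes from the documents. On this slow ramp a 0.2 s delay is a minor artefact: about 6% to 14% at n=20 and 6% to 21% at n=35 over SDs of 0.5 to 2.0 °C, against 5% with no delay. A 1 s delay matters more, at about 19% to 99% at n=20 and 30% to nearly 100% at n=35. The high figures need both a long delay and a small SD. Numbness and inattention are not quantified here.

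The finding does not show that such an effect is likely, or that the rating endpoint is compromised by press timing. It is worth fixing because the data are already to be collected and the change is small.

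**What to change.** In section 12.0, before unblinding:

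1. Keep the tolerance and pain-rating analyses as planned.
2. Name sensory threshold as a negative control.
3. Report the real-versus-sham change, with confidence intervals, for all three thresholds.
4. Add tolerance change minus sensory-threshold change as a supportive contrast.
5. State the reading in advance. A tolerance rise is interpreted as pain-specific when the contrast or the fixed-temperature ratings support it, noting that ratings alone do not exclude numbness or inattention. If all three thresholds rise alike, report that a general sensory or response effect cannot be excluded.

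The cost is a few sentences and one derived variable, with no new data or visits. The drawback is the possible loss of precision shown in step 5 of the working. The contrast also cancels only a delay common to both measures. For both reasons it should guide interpretation and leave the tolerance test in place.

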3.0 Intervention to be studied – Low intensity Focused Ultrasound Pulses (LIFUP)

(Note, although we will be using MRI scanning and thermal pain assessments, those are established techniques with low risk. The MUSC IRB is quite familiar with those. I will thus concentrate on LIFUP.)

LIFUP uses a single large concave, or multiple ultrasound transducers in a cap placed on the scalp to produce high frequency (100Hz) sonications for 30 seconds at a time for 10 trains of pulses. Unlike traditional diagnostic ultrasound, which constantly transmits ultrasound and 'listens' to the echo to form an image, LIFUP delivers the ultrasound in packets or pulses. For reasons that are not clear, pulsed ultrasound causes neurons to depolarize and fire. Bones typically block ultrasound waves. Cleverly, however, one can deliver the ultrasound from multiple sources and use the skull as a lens, to actually shape and focus the convergent beam deeper in the brain.

The clinical use of LIFUP thus uses MRI scans taken before stimulation to position and calculate how multiple ultrasonic pulsations will converge at a location in the brain (taking into account the bone dispersion of the beam from the skull). Since a small transducer like in diagnostic ultrasound cannot individually cause neuronal discharge, with LIFUP neuronal firing can be focused both deep (2-12cm under the cap; for comparison, traditional TMS can stimulate 1-3.4cm² deep^(9, 10)) and focally (as small as 0.5mm in diameter, and up to 1000mm; the facility of a standard, commercially-available 70mm figure-of-8 TMS coil is roughly 50mm²^(9, 10)). Interestingly, the pulse width of the carrying frequency of LIFUP (0.5ms) is strikingly similar to that used in all other pulsed neuromodulation therapies (DBS: 0.6ms, ECT: 0.5ms; TMS: 0.2ms; VNS: 0.5ms), suggesting that this timeframe is mechanistically meaningful. This is a good example of the common background science of brain stimulation that transcends the individual methods.

Researchers have examined the effects of LIFUP in preclinical and clinical settings, confirming its ability to safely stimulate neural tissue⁽¹¹⁻¹⁴⁾, proposing cellular mechanisms for its efficacy⁽¹³⁻¹⁹⁾, and now using LIFUP in human patients⁽²⁰⁾. Monti et al. (2016) described a case study in which they used LIFUP to stimulate a comatose patient's thalamus.⁽²⁰⁾ Two pre-LIFUP assessments rated the patient as being in minimally conscious state (MCS). After sonication, the patient recovered motor and oromotor functions the next day, advancing to full language comprehension and communication by nodding and shaking his head. Five days post-LIFUP, the patient attempted to walk. While this study was neither blinded nor sham-controlled, the first application of therapeutic LIFUP in a human patient was encouraging and we expect more therapeutic applications of LIFUP and potential clinical trials in the future. If LIFUP continues to show clinical potential, it has the potential to supplant the role of DBS without the need for surgery. The key barrier to LIFUP replacing DBS for clinical applications is that by and large, DBS is used in a manner where the device is inserted and turned constantly on without attempting to fundamentally change circuit dynamics or behavior so that you could remove the device. Obviously, patients cannot permanently wear a LIFUP helmet. However, to the degree that we learn how to stimulate in ways that permanently change circuit behavior (LTD or LTP) without ablation, we may be able to substitute several sessions of LIFUP that can train and rewire the brain instead of permanently implanting hardware. LIFUP can certainly stimulate deep and focal and noninvasively and thus may be a key next step in the field of brain stimulation.

Information on the intervention to be studied.

We will be using the Brainsonix Low intensity focused ultrasound pulsation device. (BX Pulsar 1001). Please see the manufacturers description (Technical Summary) along with appendixes about the actual safety of the device itself.

FDA Status of the BX Pulsar 1001 device.

The BX Pulsar device was initially tested at UCLA in epilepsy patients. This research required an FDA IDE, which I have attached to the IRB application. After this study was done and safety was established, the UCLA IRB now does not require an IDE and treats this form of ultrasound just like it does regular diagnostic ultrasound, which is non-significant risk. The diagnostic ultrasound devices and this one are the same in terms of what they can produce. I have attached the letters of approval from the UCLA for using this device in testing memory, Alzheimer's disease, coma, the amygdala and emotions, and the thalamus with healthy controls. I have also attached a list of FDA cleared devices.

Importantly, this device can only deliver the power of a diagnostic ultrasound device. It is not able to deliver the power needed for High Intensity Ultrasound Ablation such as is used in neurosurgery. This would require multiple machines, precisely focused, delivering over 1000 times more energy than we are using.

The PI wearing the device (puck) (not connected to the source) demonstrating the position used to reach the thalamus.

For device trials, describe the proposed use of the device as well as its safety.

We will use the device in its intended fashion. We will initially obtain a structural scan of the subjects head. We will then place the ultrasound transducer (sometimes called a puck, as it looks like a hockey puck), on the subjects head using anatomical landmarks as well as Brainsight which we know generally position the device in the correct orientation. We will then take an MRI scan of the brain.

The gel that we use between the puck and the skull is able to be seen easily on the scout MRI scan. We can then use MRI guided measurements to adjust the puck in order to position it to be able to stimulate the thalamus. This approach has been used by the UCLA group in their initial epilepsy and now healthy control and other disease studies.

We will then activate the MRI scanner and thermal pain system and then apply LIFUP or not and measure whether there are changes in pain threshold during LIFUP.

With respect to safety, the device is manufactured to certain safety parameters and will not fail or overheat or leak noise. After the initial studies in epilepsy patients, on top of the extensive animal studies, the FDA has now allowed the device to be sold and distributed. The UCLA IRB

[figure not shown]
now realizes that the device is as safe as diagnostic ultrasound.

One way of conceptualizing the issue of safety of LIFUP is as follows.

- 1) Diagnostic ultrasound is deemed safe, with only minimal limits and concerns.
- 2) Diagnostic ultrasound is sometimes used almost continuously for 30 minutes to an hour.
- 3) LIFUP is not able to deliver intensities much greater than diagnostic ultrasound.
- 4) The amount of time LIFUP is delivered (30 sec) is much less than diagnostic ultrasound.

5) Thus the amount of energy delivered is much less than diagnostic ultrasound.

6) High Intensity Ablative Ultrasound delivers energy that is 100 times greater than LIFUP.

Bushberg et al., The essential physics of medical imaging, 2nd edition (p. 553)

Why it is important to develop a non-opiate method of treating pain. Though safe and successful in most clinical settings, opioid anesthetics are limited by dose-dependent side effects and potential abuse (21). Past data indicate that risk of fatal opiate overdose is directly related to maximum prescribed daily dose (22). Moreover, studies of opiate abuse have shown that emergency room visits and fatal poisonings caused by nonmedical use of opioid analgesics have more than doubled and tripled, respectively, within the last decade (23, 24). These morbidity and mortality data demonstrate an urgent need to discover adjunctive therapies for pain management.

Brain stimulation methods are a promising avenue for neurological therapeutics in the area of pain management (5). Low Intensity Focused Ultrasound Pulsation (LIFUP) is a relatively new medical technology platform capable of neuromodulating regions of interest of the brain with high precision. Recent studies show LIFUP as a safe and effective means for neuromodulation in pathologies such as trauma and epilepsy (6-7). Additionally, focused ultrasound has been shown to induce reversible physiological effects on the nervous system, ranging from increased excitation in regions of interest to suppression of visual evoked potentials (8-9). Importantly, previous studies observed both excitation and inhibition of neuronal circuitry without characteristic physiological changes within the sonicated area such as cavitation or heat damage (10-13). Extrapolating off past studies, LIFUP may have a modulatory effect on the neuronal circuitry involved with pain, specifically when it is applied to the anterior nuclei of the thalamus, which is an important part of the pain circuit (14). Precise laboratory studies will disclose the circumstances under which LIFUP produces analgesia. The first step toward appraising LIFUP as a therapy for pain management is to determine if LIFUP produces analgesia through suppression of the anterior thalamus. Neurosurgical lesioning the anterior thalamus has been used for many years as an invasive and risky treatment for pain.

One way to diminish the risks associated with opioid analgesics is to develop therapies that reduce the dose or frequency of opiate prescriptions. Thalamic suppression via LIFUP might eventually evolve into a treatment. Regardless, this study will demonstrate a proof of concept about this new technology and its ability to influence brain circuitry and behavior. This study will be one of the first to address this limitation. On a basic science level, this study will reveal important clues about the link between regional brain activity, nociception and pain. In this sense, LIFUP is an interventional tool with which to stimulate the thalamic networks in order to evaluate its functional connections and their relevance to pain. On a clinical level, this study will contribute to the evaluation of thalamic LIFUP as an interventional tool for pain. The importance of this last goal cannot be overstated given rising opiate abuse and the extent to which chronic and postoperative pain remains undertreated (25, 26).

4.0 Study Endpoints – Overall we will test whether thalamic LIFUP during a pain provocation is safe and feasible. In addition, we will test the following endpoints.

4.1. Primary endpoint: Thalamic LIFUP will modulate pain ratings measured by administering cutaneous hot and cold stimuli via the Medoc Pathway System.

4.2. Secondary endpoints: Thalamic LIFUP will reduce BOLD activity in the thalamus.

